2.7.2. PFS. LOCAL ASSESSMENT. PP

Table 52. Progression-free survival at 12 and 24 weeks according to cohorts (local assessment. PP)

Progression-free survival	N events	N patients at risk	% Estimated cumulative survival ratio			95% CI	
at 12 weeks	Cohort A						
	Cohort B						
at 24 weeks	Cohort A						
	Cohort B						
	Strategy	N (%) events	Median (weeks)	Min-Max	Standard error	95% CI	p-value ¹
Progression-free survival	A						
	B						
	Total						

1: Log-rank test

Figure 2. Progression-free survival according to cohorts (Local assessment PP). Kaplan-Meier curve.

Table 53. Progression during follow-up (local. PP)

	Cohort A	Cohort B	Total	p-value
	N (% , 95% CI)	N (% , 95% CI)	N (% , 95% CI)	
Progression-free survival				
	PD			
	Alive: Free of progression			
	Total			

1: Pearson Chi-square; 2: Fisher's exact test

Table 54. Types of progressions / censorship during follow-up (local. PP)

	Cohort A	Cohort B	Total	p-value
	N (% , 95% CI)	N (% , 95% CI)	N (% , 95% CI)	
Progression-free survival				
	Progression-Disease			
	progression Clinical progression			
	Alive without PD at the end of follow-up			
	Alive without PD: censored by surgery			
	Alive without PD: abandonment due to patient decision			

GEIS-30 STUDY

Statistical analysis plan

Total

1: Pearson Chi-square; 2: Fisher's exact test

Table 55. Time to PD (weeks) (Local. PP)

	Cohort A			Cohort B			Total			p-value ¹
	N	Mean (SD)	Median (Min-Max)	N	Mean (SD)	Median (Min- Max)	N	Mean (SD)	Median (Min-Max)	
Time to PD (weeks)										

1: Mann-Whitney U test

2.7.3 PFS. CENTRAL ASSESSMENT. ITT

To describe the event in PFS, the protocol will be followed:

“Overall progression-free survival will be calculated from the date of initiation of treatment to the first date of documented progression or date of death, whatever the cause. Live patients with no evidence of progression at the time of analysis will be censored on the date of the last follow-up. ”

Table 56. Progression-free survival at 12 and 24 weeks according to cohorts (Central assessment. ITT)

Progression-free survival	N events	N patients at risk	% Estimated cumulative survival ratio	95% CI		
at 12 weeks	Cohort A					
	Cohort B					
at 24 weeks	Cohort A					
	Cohort B					
	Strategy	N (%) events	Median (weeks)	Min-Max	Standard error	p-value ¹
Progression-free survival	A					
	B					
	Total					

1: Log-rank test

Figure 3. Progression-free survival according to cohorts (Central assessment ITT). Kaplan-Meier curve.

GEIS-30 STUDY

Statistical analysis plan

Table 57. Progression during follow-up (Central assessment. ITT)

	Cohort A		Cohort B		Total	p-value
	N (% , 95% CI)		N (% , 95% CI)		N (% , 95% CI)	
Progression-free survival	PD					
	Alive: Free of progression					
	Total					

1: Pearson Chi-square; 2: Fisher's exact test

Table 58. Time to PD (weeks) (Central assessment. ITT)

	Cohort A			Cohort B			Total		p-value ¹
	N	Mean (SD)	Median (Min-Max)	N	Mean (SD)	Median (Min-Max)	N	Mean (SD)	
Time to PD (weeks)									

1: Mann-Whitney U test

Table 59. Follow-up time (weeks) (Central assessment. ITT)

	Cohort A			Cohort B			Total		p-value ¹
	N	Mean (SD)	Median (Min-Max)	N	Mean (SD)	Median (Min-Max)	N	Mean (SD)	
Follow-up time (weeks)									

1: Mann-WhitneyU test

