#### **10.1.2. Secondary Endpoints**

##### **Overall progression free survival (median PFS)**

Overall progression free survival will be computed from the date of start of treatment to the first documented date of progression or the date of death, whatever the cause. Patients alive and free from progression at the time of the analysis will be censored at the date of last follow-up.

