2.8. EFFICACY:ENDPOINT SECONDARY GLOBAL SURVIVAL (OS)

2.8.1. OS. ITT

Table 63. Overall survival at 12 and 24 weeks according to cohorts (ITT)

Overall survival	N events	N patients at risk	% Estimated cumulative survival ratio	95% CI			
at 12 weeks	Cohort A						
	Cohort B						
at 24 weeks	Cohort A						
	Cohort B						
Overall survival	Strategy	N (%) events	Median (weeks)	Min-Max	Standard error	95% CI	p-value ¹
Overall survival	A						
	B						
	Total						

1: Log-rank test

Figure 5. Overall survival according to cohorts (ITT). Kaplan-Meier curve.

Table 64. Exitus during follow-up and at 12 weeks (ITT)

	Exitus	Cohort A	Cohort B	Total	p-value
		N (%), 95% CI)	N (%), 95% CI)	N (%), 95% CI)	
Overall survival	Live				
	Loss Follow-up				
	Total				
	Reason Exitus				
Reason Exitus	No				
	Disease progression				
	Kidney failure				
	Clinical deterioration				
	Post-surgical complications				
	Unknown				
	Total Overall				
survival at 12 weeks	Exitus				
	Live				
	Total				

1: Pearson Chi-square; 2: Fisher's exact test

Table 65. Time to exit (weeks) (ITT)

	Cohort A			Cohort B			Total			p-value ¹
	N	Mean (SD)	Median (Min-Max)	N	Mean (SD)	Median (Min-Max)	N	Mean (SD)	Median (Min-Max)	

GEIS-30 STUDY

Statistical analysis plan

Exit time
(weeks)

1: Mann-Whitney U test

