2.11. SAFETY: SAEs AND TOXICITIES

Following the criteria established in the protocol, "Any patient included in the study and who has received at least a single dose of study medication will be evaluable for toxicity analyzes."

GEIS-30 STUDY

Statistical analysis plan

AES and Toxicities Table 74. All monitoring

		Cohort A	Cohort B	Total	p-value
		N (%)	N (%)	N (%)	
AE	Yes				
	Total				
	<hr/>				
toxicity (related)	No				
	Yes				
	Total				
<hr/>					
≥3 AE grade	No				
	Yes				
	Total				
<hr/>					
toxicity grade ≥3 (related)	No				
	Yes				
	Total				
<hr/>					
SAE (at least one per patient) ³	No				
	Yes				
	Total				

1: Chi-square; 2: Fisher's exact test; 3: patients could present more than one SAE

Table 75. AEs and Toxicities with start date prior to treatment

		Cohort A	Cohort B	Total	p-value
		N (%)	N (%)	N (%)	
AE	No				
	Yes				
	Total				
<hr/>					
AE grade ≥ 3	No				
	Total				

1: Chi-square; 2: Fisher's exact test

Table 76. AEs and Toxicities during treatment

		Cohort A	Cohort B	Total	p-value
		N (%)	N (%)	N (%)	
AE	Yes				
	Total				
<hr/>					
Toxicity (related)	No				
	Yes				
	Total				
<hr/>					
AE grade ≥3	No				
	Yes				
	Total				
<hr/>					
Toxicity grade ≥3 (related)	No				
	Yes				
	Total				

1: Chi-square; 2: Fisher's exact test

Table 77. ESA and Toxicities after treatment

		Cohort A	Cohort B	Total	p-value
		N (%)	N (%)	N (%)	
AE	No				
	Yes				
	Total				

GEIS-30 STUDY

Statistical analysis plan

Toxicity (related)	No
	Yes
	Total
AE grade ≥ 3	No
	Yes
	Total
Toxicity grade ≥ 3 (related)	No
	Total

1: Chi-square; 2: Fisher's exact test

Table 78. AE and Toxicities with no known date

		Cohort A	Cohort B	Total	p-value
		N (%)	N (%)	N (%)	
AE	No				
	Yes				
	Total				
Toxicity (related)	No				
	Yes				
	Total				
AE grade ≥ 3	No				
	Yes				
	Total				
Toxicity grade ≥ 3 (related)	No				
	Total				

1: Chi-square; 2: Fisher's exact test

The frequencies of all toxicities with grade ≥ 3 are presented below.

Table 79. Frequencies of AEs grade ≥ 3

	Cohort A	Cohort B	Total
	N (%)	N (%)	N (%)
Abscess of tumor mass - Grade 3			
ALT increased - Grade 3			
Anemia - Grade 3			
Ascites - Grade 3			
AST increased - Grade 3			
Asthenia - Grade 3			
Back pain - Grade 3			
Bilirubin increased - Grade 3			
Cardiac dysrhythmia / chest pain - Grade 3			
Diarrhea - Grade 3			
Fatigue - Grade 3			
Femur fracture - Grade 3			
Gastrointestinal bleeding - Grade 5			
General Status deterioration - Grade 5			

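### The SAP's supplementary PFS status tables have no category for death without documented progression, and they test crude status between cohorts without regard to time at risk (minor)

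*SAP*

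**What the plan says.** Protocol 10.1.2 runs PFS from the start of treatment "to the first documented date of progression or the date of death, whatever the cause". SAP 2.7.3 repeats this ("to the first date of documented progression or date of death, whatever the cause") and limits censoring to the living: "Live patients with no evidence of progression at the time of analysis will be censored on the date of the last follow-up".

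Under the same PFS headings, the SAP sets out two kinds of supplementary table.

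- **Tables 49, 53, 57 and 61** give progression status over follow-up (local ITT, local PP, central ITT, central PP). Apart from the total, the rows are PD and "Alive: Free of progression".
- **Tables 50 and 54** (local ITT and PP) give types of progression and censoring. The event side covers disease and clinical progression. The other side has three groups of living patients without PD: at the end of follow-up, censored by surgery, and stopped by patient decision.

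All six have a p-value column and a Pearson chi-square/Fisher footnote. A 95% CI header is visible in Tables 53, 54, 57 and 61. Separately, Tables 48, 52, 56 and 60 give event counts, Kaplan-Meier estimates and a log-rank test.

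**The concern.** There are two defects, both in the supplementary tables.

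1. **No place for one kind of PFS event.** Under the SAP's definition, a patient who dies without documented progression has had an event and is not censored. None of the six tables has a row for that patient. Whoever fills the table must call the death PD, put it among the living, or leave it out, and each choice gives a different table.
2. **Crude status is tested as if it were complete.** The tables classify patients over a follow-up that can differ in length, and they count a patient censored early as a plain non-event. A chi-square or Fisher test on that split compares follow-up and censoring as well as PFS.

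At stake are agreement between these tables and the Kaplan-Meier tables beside them, the separation of progression from other death, and the meaning of the p-values.

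**Working it through.** The plan states no figure to reproduce here. The first check is of table structure; the arithmetic that follows only illustrates.

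**Step 1. Definition against rows.**

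| Outcome | Under SAP 2.7.3 | Tables 49, 53, 57, 61 | Tables 50, 54 |
|---|---|---|---|
| Documented progression | Event | PD | Disease or clinical progression |
| Alive, no progression | Censored | Alive row | One of three alive rows |
| Death, no documented progression | Event | No row | No row |

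The event labels of Tables 50 and 54 run together in the text as read, but nothing in them mentions death.

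**Step 2. Can such a death arise?** Yes, in principle. Protocol 5.7 stops scheduled imaging once a new anti-cancer therapy begins, so a patient can die with no progression documented on central review. Whether any did is not stated.

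**Step 3. Effect on a percentage.** The maximum cohort size is 37 (SAP 1.13.1), so one death moves a percentage by 1/37 = 2.7 points. At the first-stage size of 17 (Protocol 5.1) it is 1/17 = 5.9 points. As an assumed example, let 28 of 37 patients have a PFS event (28/37 = 75.7%), of which k are deaths without PD:

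| k | Death left out of PD, denominator kept | Death dropped from the table |
|---|---|---|
| 1 | 27/37 = 73.0% | 27/36 = 75.0% |
| 2 | 26/37 = 70.3% | 26/35 = 74.3% |
| 4 | 24/37 = 64.9% | 24/33 = 72.7% |

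Calling the deaths PD keeps 28/37 but reports deaths as progressions. A separate death row keeps 28/37 and labels each event correctly.

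**Step 4. Effect of unequal follow-up on the crude test.** With exponential PFS and median m, the proportion with an event by month t is 1 − 0.5^(t/m). Protocol 4.1 offers two medians for illustration: 3.6 months (a well-differentiated/dedifferentiated series on several regimens) and 4.6 months (the phase III pazopanib arm). The rejection rates come from simulating an uncorrected Pearson chi-square at two-sided 5%, with 37 patients per cohort, identical PFS in both and 100,000 replicates. **The follow-up pairs are assumptions.**

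| Follow-up (months) | m = 3.6: event proportions; rejection | m = 4.6: event proportions; rejection |
|---|---|---|
| 12 vs 12 | 90.1% vs 90.1%; 5.8% | 83.6% vs 83.6%; 5.2% |
| 12 vs 6 | 90.1% vs 68.5%; 65.4% | 83.6% vs 59.5%; 64.9% |
| 24 vs 12 | 99.0% vs 90.1%; 39.3% | 97.3% vs 83.6%; 58.9% |

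With equal follow-up the test is close to its nominal level. With unequal follow-up it can reject often when PFS is identical.

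**Step 5. The other end of the range.** SAP 1.15 puts the last patient's first visit in the second quarter of 2015 and the end of study at 2 March 2018, about 32 months later. If every patient was followed to that date, at m = 4.6 the proportion with an event is at least 1 − 0.5^(32/4.6) = 99.2%. Differences in follow-up could then move the split by less than one point. Early censoring for surgery or by patient decision would still be counted as non-events.

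**The case against.** **The real PFS analysis is sound.** This stands. The SAP adopts the protocol definition, and the Kaplan-Meier tables can count every event under it. The 12-week primary endpoint counts deaths as failures (SAP 2.6) and does not draw on these tables. A reader might infer that the PFS estimates or the primary result are wrong; the documents do not support that.

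**The missing row may be an empty category.** This is plausible. Other shells seem to leave out empty rows: the week 7 visit in Table 35 has only a yes row, Tables 92 and 93 lack the highest GMI category, Tables 98 and 99 lack the middle one, and Table 102 already prints a p-value. PD may also be shorthand for any PFS event. Against the second reading, the same sections tabulate time to PD, and SAP 2.9 uses it as time to progression for the GMI. The SAP states neither reading, so it cannot be said that patients will be misplaced or that counts will disagree, only that the plan does not prevent it.

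**The SAP does not show that such deaths occurred.** Correct. It is tempting to cite "Post-surgical complications" and kidney failure among the reasons for death in Table 64, or "Gastrointestinal bleeding - Grade 5" in Table 79. But Table 64 covers deaths at any time, and survival follow-up continues after progression; Table 79 does not say whether the bleed came before progression.

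**The follow-up effect is hypothetical.** Its size is. Table 59 would report follow-up by cohort, but it is an unfilled shell. The 4.6-month median comes from a trial that excluded liposarcoma. It remains true that a crude test ignores time at risk.

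**Descriptive p-values appear throughout this SAP.** They do, and removing them alters no decision, because the efficacy rule is applied within each stratum. Here, though, a log-rank test of the same comparison already stands beside them, so the crude test adds only one that can mislead.

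**Conclusion.** The point holds, and it is minor. The six tables do not match the SAP's own PFS definition, because a death without documented progression has no category. They also test crude status in a way that ignores censoring and time at risk.

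The size cannot be stated. The first defect costs 2.7 points per such death in a cohort of 37, and there may be none. For the second, the range in the working runs from under one point, if everyone was followed to the end of study, to a rejection rate of about 65% under an assumed 12 versus 6 months. Both figures assume exponential PFS with borrowed medians. The bias arises only if follow-up or early censoring differs between the cohorts.

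The CI remark applies only to Tables 53, 54, 57 and 61, since no such header is visible in Tables 49 and 50.

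**What to change.** 1. Add a row *Death without documented progression* to Tables 49, 50, 53, 54, 57 and 61.
2. Require the event rows to sum to the number of events in the matching Kaplan-Meier table: 48 for Tables 49 and 50, 52 for 53 and 54, 56 for 57, and 60 for 61.
3. Present the six tables as descriptive counts, without chi-square or Fisher p-values, and without CIs where these are shown.
4. Use the Kaplan-Meier estimates and the log-rank test for any PFS comparison.

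The cost is editing table shells. No new data are needed, and there is no other downside.

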2.7.4. PFS. CENTRAL ASSESSMENT. PP

Table 60. Progression-free survival at 12 and 24 weeks according to cohorts (Central assessment. PP)

Progression-free survival	Cohort	N events	N patients at risk	% Estimated cumulative survival ratio	Standard error	95% CI	p-value ¹
at 12 weeks	Cohort A						
	Cohort B						
at 24 weeks	Cohort A						
	Cohort B						
Progression-free survival	A						
	B						
	Total						

1: Log-rank test

GEIS-30 STUDY

Statistical analysis plan

Figure 4. Progression-free survival according to cohorts (Central assessment. PP). Kaplan-Meier curve.

Table 61. Progression during follow-up (Central assessment. PP)

	Cohort A		Cohort B		Total	p-value
	N (% , 95% CI)		N (% , 95% CI)		N (% , 95% CI)	
PD						
Progression-free survival	Alive: Free of progression					
	Total					

1: Pearson Chi-square; 2: Fisher's exact test

Table 62. Time to PD (weeks) (Central assessment. PP)

	Cohort A			Cohort B			Total		p-value ¹
	N	Mean (SD)	Median (Min-Max)	N	Mean (SD)	Median (Min- Max)	N	Mean (SD)	
Time to PD (weeks)									

1: Mann-Whitney U test

GEIS-30 STUDY

Statistical analysis plan

2.8. EFFICACY:ENDPOINT SECONDARY GLOBAL SURVIVAL (OS)

2.8.1. OS. ITT

Table 63. Overall survival at 12 and 24 weeks according to cohorts (ITT)

Overall survival	N events	N patients at risk	% Estimated cumulative survival ratio	95% CI			
at 12 weeks	Cohort A						
	Cohort B						
at 24 weeks	Cohort A						
	Cohort B						
Overall survival	Strategy	N (%) events	Median (weeks)	Min-Max	Standard error	95% CI	p-value ¹
Overall survival	A						
	B						
	Total						

1: Log-rank test

Figure 5. Overall survival according to cohorts (ITT). Kaplan-Meier curve.

Table 64. Exitus during follow-up and at 12 weeks (ITT)

	Exitus	Cohort A	Cohort B	Total	p-value
		N (%), 95% CI)	N (%), 95% CI)	N (%), 95% CI)	
Overall survival	Live				
	Loss Follow-up				
	Total				
	Reason Exitus				
Reason Exitus	No				
	Disease progression				
	Kidney failure				
	Clinical deterioration				
	Post-surgical complications				
	Unknown				
	Total Overall				
survival at 12 weeks	Exitus				
	Live				
	Total				

1: Pearson Chi-square; 2: Fisher's exact test

Table 65. Time to exit (weeks) (ITT)

	Cohort A			Cohort B			Total			p-value ¹
	N	Mean (SD)	Median (Min-Max)	N	Mean (SD)	Median (Min-Max)	N	Mean (SD)	Median (Min-Max)	

GEIS-30 STUDY

Statistical analysis plan

Exit time
(weeks)

1: Mann-Whitney U test

2.8.2. OS. PP

Table 66. Overall survival at 12 and 24 weeks according to cohorts (PP)

Overall survival	N events	N patients at risk	% Estimated cumulative survival ratio			95% CI	
			Min-Max	Standard error	p-value ¹		
at 12 weeks	Cohort A						
	Cohort B						
at 24 weeks	Cohort A						
	Cohort B						
	Strategy	N (%) events	Median (weeks)	Min-Max	Standard error	95% CI	p-value ¹
Overall survival	A						
	B						
	Total						

1: Log-rank test

Figure 6. Overall survival according to cohorts (PP). Kaplan-Meier curve.

Table 67. Exitus during follow-up and at 12 weeks (PP)

		Cohort A	Cohort B	Total	p-value
		N (%), 95% CI)	N (%), 95% CI)	N (%), 95% CI)	
Overall survival	Exitus				
	Live				
	Loss Follow-up				
	Total				
Reason Exitus	No				
	Disease progression				
	Kidney failure				
	Clinical deterioration				
	Post-surgical complications				
	Unknown				
	Total Overall				
survival at 12 weeks	Exitus				
	Live				
	Total				

1: Pearson Chi-square; 2: Fisher's exact test

GEIS-30 STUDY

Statistical analysis plan

Table 68. Time to exit (weeks) (PP)

	Cohort A			Cohort B			Total		p-value ¹
	N	Mean (SD)	Median (Min-Max)	N	Mean (SD)	Median (Min-Max)	N	Mean (SD)	
Exit time (weeks)									
1:					Mann-Whitney				U-test

GEIS-30 STUDY

Statistical analysis plan

2.9. GMI: GROWTH MODULATION INDEX

Following the definition in the protocol, the GMI will be calculated as "the ratio between time to progression with pazopanib (TTPp) divided by time to progression with the previous line of treatment (TTPp-1)".

The time to PD with pazopanib is presented in the section EFFICIENCY: MAIN ENDPOINT and the duration of the previous chemotherapy until relapse is presented in Table 30. Number of cycles and duration of the previous chemotherapy.

Table 69. Growth modulation index (GMI) (ITT)

	Cohort A			Cohort B			Total			p-value ¹
	N	Mean (SD)	Median (Min-Max)	N	Mean (SD)	Median (Min-Max)	N	Mean (SD)	Median (Min-Max)	
Growth modulation index (GMI)										

1: Mann-Whitney U test

Table 70. Categorized GMI (ITT)

	Cohort A	Cohort B	Total	p-value
	N (%)	N (%)	N (%)	
GMI categorized				
<1				
1-1.33				
> 1.33				
Total				

1: Chi-square; 2: Fisher's exact test

Table 71. Growth modulation index (GMI) (PP)

	Cohort A			Cohort B			Total			p-value ¹
	N	Mean (SD)	Median (Min-Max)	N	Mean (SD)	Median (Min-Max)	N	Mean (SD)	Median (Min-Max)	
Growth modulation index (GMI)										

1: Mann-Whitney U test

Table 72. Categorized GMI (PP)

	Cohort A	Cohort B	Total	p-value
	N (%)	N (%)	N (%)	
GMI categorized				
<1				
1-1.33				
> 1.33				
Total				

1: Chi-square; 2: Fisher's exact test

GEIS-30 STUDY

Statistical analysis plan

2.10. ECOG EVOLUTION

Table 73. ECOG evolution during treatment (ITT)

		Cohort A	Cohort B	Total	p-value ¹
		N (%)	N (%)	N (%)	
Performance Status ECOG (baseline)	0				
	1				
	Total				
Performance Status ECOG Day 1	0				
	1				
	Total				
Performance Status ECOG Week 1	0				
	1				
	2				
Performance Status ECOG Week 3	0				
	1				
	2				
Performance Status ECOG Week 5	0				
	1				
	2				
Performance Status ECOG Week 7	0				
	1				
	2				
Performance Status ECOG Week 9	0				
	1				
	2				
Performance Status ECOG Week 12	0				
	1				
	Total				
p-value ³	Basal vs. day 1				
	Basal vs. week 1				
	Basal vs. week 3				
	Basal vs. week 5				
	Basal vs. week 7				
	Basal vs. week 9				
	Basal vs. week 12				

1: Pearson's Chi-square; 2: Fisher's exact test; 3: Marginal homogeneity test

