### **4. Physical Exam:**

**4.1 Pre-treatment (Screening):** Evaluation by body system, height, weight, body surface area (BSA) and measurement of vital signs (blood pressure and body temperature).

**4.2 During treatment and follow up visits:** Evaluation by body system, weight, body surface area (BSA) and verification of patient blood pressure measurements, every treatment visit before study drug administration and at every visit and follow-up visit.

**5. ECOG Performance Status (PS):** PS will be assessed at screening, at day 1 before the study drug is administered, and in week 1, 3, 5, 7, 9 and week 12. Thereafter, every treatment visit before the study drug is administered (4 weeks).

If subjects discontinue study treatment without disease progression (e.g., withdrawal of study treatment due to unacceptable toxicity), continue the assessments of ECOG PS in accordance with the disease assessments until subjects experience disease progression.

**6. Concomitant Medication:** The use of any natural/ herbal products or others “folk remedies” should be discouraged but use of these products, as well as use of vitamins or nutritional supplements and all others concomitant medications must be recorded in the Case Report Form (CRF). Any medications, with the exception noted in the section (additional details), which are considered necessary for patient’s welfare, and which it is believed will not interfere with the study medication, may be given at the discretion of the Investigator, providing the medication, doses, dates and reasons for administration in the CRF.

**7. Adverse Events:** The CTC-AE version 4.0 will be used to evaluate the clinical safety of the treatment in this study. Subjects will be assessed for AEs at each clinical visit and as necessary throughout the study.

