2.3. ITT and PP POPULATIONS

To determine ITT and PP populations, the definitions specified in the protocol will be followed:

- Analysis by Intention to Treat (**ITT**): Efficacy analyses will be calculated on the population by intention to treat. All patients participating in the study will be included in the efficacy analysis.
- Analysis by Protocol (**PP**): Efficacy analyses will be calculated on the protocol population. All patients participating in the study and who have received at least 3 weeks of treatment with Pazopanib (without major protocol deviations) will be included in the efficacy analysis.

Table 36. ITT and PP Populations

		Cohort A	Cohort B	Total	p-value
		N (%)	N (%)	N (%)	
ITT population	Yes				
	Total				
Duration tt Pazopanib (weeks)	<3 weeks				
	≥3 weeks				
	Ongoing (no end date of tt)				
Total					
Population PP	No				
	Yes				
	Total				

1: Chi-square; 2: Test Fisherexact

Pacientes with less than 3 week of pazopanib treatment:

Table 37. Patients with duration of pazopanib <3 weeks

Study Subject ID	Cohort	PP population	Reason excluded from PP population	Tx Pazopanib duration (days)

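### The ECOG table is labelled ITT, but its paired tests can use only patients with a value at that visit, so a stable result may reflect loss of deteriorating patients

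*SAP*

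**What the plan says.** SAP section 2.10 contains one table, "Table 73. ECOG evolution during treatment (ITT", with no per-protocol counterpart. Section 2.3 defines the ITT set without exceptions: "All patients participating in the study will be included in the efficacy analysis".

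The table gives ECOG counts by cohort at baseline, day 1 and weeks 1, 3, 5, 7, 9 and 12. Below them are seven within-patient p-values, from baseline against day 1 through to "Basal vs. week 12". The footnote names the method: "3: Marginal homogeneity test". The SAP does not say how a missing ECOG value is handled.

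The rows differ by visit:

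- "Performance Status ECOG (baseline") and day 1: grades 0 and 1, and a total.
- Weeks 1, 3, 5, 7 and 9 (for example "Performance Status ECOG Week 9"): grades 0, 1 and 2.
- "Performance Status ECOG Week 12": grades 0 and 1, and a total.

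No visit has a row for ECOG 3-4, dead or not assessed.

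The protocol settles who has a value. RECIST progression ends treatment (6.3.1). For patients who stop without progressing, section 8.2 item 5 asks sites to "continue the assessments of ECOG PS in accordance with the disease assessments until subjects experience disease progression". After progression, section 5.6.3 lists only survival, patient status and new anti-cancer therapy. The table of assessments has no ECOG at the 28-day visit or in the after-progression column.

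**The concern.** An ITT label tells the reader that the result describes everyone enrolled. A paired test with no missing-data rule describes only those who have both measurements. Here the reason for having no later measurement is usually progression or death, and those patients are the likeliest to have declined. A non-significant week-12 comparison could then be read as performance status being maintained on pazopanib when it describes only those who remained.

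The row structure adds to this. A patient who has died, was not assessed, or is at ECOG 3-4 has no line in the table, so the loss is not visible where the p-values are reported. The contrast with the primary endpoint is marked: there, unknown status counts as failure (Protocol 10.1.1, SAP 2.6), which keeps every patient in the denominator. ECOG has no equivalent rule.

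**Working it through.** **1. The plan's own figure.** The documents give no number for ECOG, but the size estimate below borrows P0 = 20% and P1 = 40% from Protocol 10.4, so that design was checked first. It enrols 17 patients, stops at 3 or fewer successes, continues to 37, and is positive at 11 or more.

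- P(positive | p) = sum over x = 4 to 17 of P(X1 = x) × P(X2 ≥ 11 − x), with X1 ~ Bin(17, p) and X2 ~ Bin(20, p).
- p = 0.20 gives 0.0948; p = 0.40 gives 0.9033.

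Both agree with the stated 10% error rates. The design is not in dispute.

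**2. Who can enter a paired test.** A marginal homogeneity test compares two values from the same patient.

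| Patient's situation | ECOG scheduled? | Can enter the week-12 test? |
|---|---|---|
| On treatment | Every visit | Yes |
| Stopped, not progressed | With disease assessments | Yes, if assessed then |
| Progressed before week 12 | No | No |
| Died before week 12 | No | No |

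A patient first found to have progressed at the week-12 visit can still contribute, because ECOG and imaging are both scheduled then.

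**3. How many could be missing at week 12.** Inputs: S(12) = 0.20 or 0.40; scans at weeks 7 and 12. Assumptions: progression is exponential; all primary-endpoint failures are progressions or deaths; patients progressed by the week-7 scan have no later ECOG. Then S(7) = S(12)^(7/12).

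- S(12) = 0.20: S(7) = 0.20^(7/12) = 0.39, so 61% have progressed. In a cohort of 37 that is 37 × 0.61 ≈ 22.6 patients.
- S(12) = 0.40: S(7) = 0.40^(7/12) = 0.59, so 41% have progressed. In a cohort of 37 that is 37 × 0.41 ≈ 15.2 patients.

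**4. Whether the handling of leavers can matter.** This step uses invented counts, to show sensitivity only. Take 37 patients, 15 with a week-12 value (2 worse, 1 better) and 22 without. Apply the exact McNemar test, the two-category form of marginal homogeneity: p = 2 × P(X ≤ 1), X ~ Bin(worse + better, ½), capped at 1. Suppose no leaver improved.

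| Leavers counted as worse | Worse / better | p |
|---|---|---|
| 0 (observed pairs only) | 2 / 1 | 1.00 |
| 6 of 22 | 8 / 1 | 2 × (1 + 9)/2^9 = 0.039 |
| 11 of 22 | 13 / 1 | 2 × (1 + 14)/2^14 = 0.0018 |
| 22 of 22 | 24 / 1 | 2 × (1 + 25)/2^25 < 0.0001 |

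The conclusion can reverse on a choice that the SAP leaves unstated. The example says nothing about what the true decline is.

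**The case against.** The best defence has five parts.

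- **Worsening is visible.** Entry requires ECOG 0-1, so every value in the ECOG 2 rows at weeks 1 to 9 is a decline, and shifts from 0 to 1 also show. This stands. A reader might infer that the table has no place for worse status at all; that is wrong for those five visits.
- **The missing week-12 row is weak evidence.** Other SAP tables also omit levels: Table 35 has no negative row for baseline or week 7, and Tables 92-93 and 98-99 drop GMI categories. A line may also have been lost in reading the PDF. This stands. A reader might infer that an ECOG of 2 at week 12 would be discarded, but no text says so. The point does not depend on that row.
- **The title limits scope to the treatment period, and ITT is only the tag that separates this set from per protocol.** This stands in part: restriction to patients with data is inferred from the test, not written. But section 2.10 has no per-protocol version to be told apart from, and an on-treatment comparison should carry that name.
- **Departures are reported elsewhere.** Table 35 gives visit completion, Table 64 gives deaths, and the PFS tables give progression. True, but none of these is linked to Table 73, and none changes which patients the p-values describe.
- **The stakes are small.** ECOG evolution is not a listed objective or defined endpoint, and safety is defined through adverse events, examinations, vital signs and laboratory tests. This stands and limits the severity.

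**Conclusion.** The point holds as a minor one. As written, the plan yields observed-case paired tests under an ITT label, with loss that depends on outcome and no row showing who is absent. A stable result may therefore reflect the loss of deteriorating patients; the documents do not show that it will.

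About 41-61% of patients could lack a week-12 value, given the design's 20% and 40% rates and the assumptions in the working, of which exponential progression is the main one. A figure of 60-80% absent would need every patient not progression free at week 12 to have no value, which the schedule does not support, since progression first seen at that visit comes with an ECOG assessment.

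A reader might go further and infer that most patients decline unseen. The documents give no ECOG decline rate for those who stay or for those who leave, so the size of any hidden decline cannot be derived. Treatment stops on RECIST progression, and nothing in the documents ties it to a particular ECOG change. The primary decision rule is untouched.

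**What to change.** In SAP section 2.10:

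- Keep all ITT patients in the denominator at every visit and show the number assessed.
- Use the same rows throughout: 0, 1, 2, 3-4, dead, and not assessed with the reason.
- Relabel the seven paired tests as covering patients with data at both visits, or drop the p-values.
- Optionally, add a sensitivity analysis that counts death as worsening and, separately, loss after progression as worsening. Keeping the two apart matters because the second mixes a RECIST event with performance status and partly repeats the PFS tables.

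The cost is table wording and a little extra programming, and the table will probably look less favourable. No new data collection is needed.
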